TITLE	EXAMINING THE FEASIBILITY AND ACCEPTABILITY OF SAUNA SESSIONS AND COGNITIVE BEHAVIORAL THERAPY (CBT) FOR PARTICIPANTS WITH CLINICAL DEPRESSION
SPONSOR	[name]
CO-SPONSOR	[name]
NUMBER OF SITES	1
RATIONALE	Depression recovery is not uniformly linear; people who recover from depression often experience acute improvements, termed ‘sudden gains,’ early in treatment. Data suggest that participants with clinical depression who receive whole body heating (Hanusch et al., 2013; Janssen et al., 2016) and participants who receive cognitive behavioral therapy (CBT) treatment (Aderka et al., 2012; Tang et al., 1999) show sudden gains. Ascertaining if a treatment comprising both sauna sessions and CBT sessions is feasible and tolerable will allow for further research of this integrative mind-body treatment as a potentially effective and disseminable treatment for clinical depression.
STUDY DESIGN	Randomized, blinded pilot trial

PRIMARY OBJECTIVE	Pilot RCT procedures: We will conduct a pilot trial ($N=30$) to test the feasibility and acceptability of recruitment, retention, and randomization procedures in preparation for a larger efficacy trial of WBH+CBT. We will randomize participants with clinical depression to receive 8 weekly CBT + 4 biweekly active sauna sessions (refined during Aim 1) or 8 weekly CBT + 4 biweekly sham sauna sessions. After the first half of enrollment ($n=15$) is complete, we will use participant and staff feedback to refine procedures for the remaining enrollment (we will submit any refinements or changes to the treatment to the UCSF IRB approval before implementing them).
SECONDARY OBJECTIVES	To pilot test the feasibility of all assessment procedures in anticipation of a larger trial.
NUMBER OF PARTICIPANTS	30

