PARTICIPANT SELECTION CRITERIA	
Inclusion Criteria:
 
 1. Age of at least 18 years old 2. Current major depressive episode of at least 2 weeks duration as assessed by the Structured Clinical Interview for DSM-5 (SCID) and a Beck Depression Inventory-II (BDI-II) score ≥ 21 at screening 3. Able to understand the nature of the study and able to provide written informed consent prior to conduct of any study procedures 4. Must have smartphone onto which they can download an app from Apple App or Google Play stores 5. Ability to lie supine (on back) for 2 hours (required for sauna sessions) 6. Must be fully vaccinated against COVID-19 
Exclusion Criteria:
 
 1. $>30\%$ reduction in BDI-II score between Screen #1 and Screen #2 (conducted ~ 1 week after Screen #1). 2. Suicide attempt in the past 12 months defined using the SAMHSA suicidality question during the clinician-administered interview or active suicidal ideation as indexed by a score of 3 on the BDI-II suicidality item during the clinician-administered interview. 3. Any of the following medical conditions: cardiovascular disease (other than controlled hypertension), seizure disorder, history of cerebrovascular accident (CVA) or other serious neurological condition (e.g. Parkinson's disease, multiple sclerosis, or dementia), current neoplasia, any active enclosed infection (e.g. dental abscess, joint infection), hemophilia or other cause for excessive bleeding (e.g. platelet disorder), or other medical

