	
12. Unwilling to refrain from heavy exercise on the day of sauna sessions
 
13. Unwilling to refrain from engaging with sauna, hot yoga, cold plunges, cryotherapy, and hot tub/jacuzzi outside of study (prospective participant must not have engaged with any of these activities for 30 days prior to their baseline study visit).
 
14. Has begun new psychotherapy treatment in the prior 6 weeks
 
*Note: All medications reported by potential subjects will be reviewed by medical monitor [name]. If the medication is determined to not have meaningful impacts on bodily thermoregulatory processes and to not interact with whole body heating, the subject may participate.

TEST PRODUCT, DOSE, AND ROUTE OF ADMINISTRATION	Portable Sauna Dome – One Person Supine sauna device, head out, body inside of sauna Sauna session approx. 80 – 140 minutes, maximum 140 minutes Manufactured by Clearlight Infrared
CONTROL PRODUCT, DOSE AND ROUTE OF ADMINISTRATION	All participants receive cognitive behavioral therapy (CBT), and 50% of participants receive active sauna sessions while 50% receive sham sauna sessions (the test product treatment listed above, Portable Sauna Dome)
DURATION OF PARTICIPANT PARTICIPATION AND DURATION OF STUDY	
This is a single-center, two-arm, randomized experimental study that will include 30 participants. Participants will be in the study for approximately 10 weeks. Total time involved will be approximately ~34 hours:
 
 • E-Screen: Web-based eligibility screen for self-report eligibility criteria 
 ○ ~10 minutes • Phone Screen: Phone call to review eligibility, verify shipping address for Oura ring sizing kit and schedule baseline study visits 
 ○ ~25 minutes • In-Person Screen / Baseline Visit: Participant to complete screening procedures, provide informed written consent and receive bill of rights, download Oura ring app, complete self-report questionnaires, anthropometric assessments, schedule study visits. Randomization to receive either active sauna sessions or sham sauna sessions. 
 ○ ~220 minutes • Weekly depression survey: Web-based surveys assessing depression symptoms on Mondays. 
 ○ ~ 10 minutes each

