	
 • Sauna Visits 1-4: In-person visits, participant (if female) to complete pregnancy screen if the participant thinks there is a possibility of pregnancy, COVID-19 rapid test, complete questionnaires (all sauna visits), provide saliva samples (Sauna Visits 1 and 4) and blood samples (Sauna Visit 1, Sauna Visit 4 if the participant chooses), and complete sauna session 
 ○ ~220-240 minutes each • Cognitive Behavioral Therapy (CBT) Visits 1-8: In-person visits, participant to receive 50-minute CBT session and complete self-report measures 
 ○ ~65 minutes each • Closeout Visit: In-person visit, participant to complete questionnaires, complete clinician-administered assessment, provide blood and saliva samples, and return Oura ring. 
 ○ ~60 minutes
CONCOMMITANT MEDICATIONS	
Allowed:
 
 • All medications reported by potential participants will be reviewed by medical monitor [name]. If the medication is determined to not have meaningful impacts on bodily thermoregulatory processes and to not interact with whole body heating, the participant may participate. 
Prohibited:
 
 1. Use of any medication that might impact thermoregulatory capacity, including: diuretics, barbiturates, beta-blockers, antipsychotic agents, anti-cholinergic agents or chronic use of antihistamines, cytokine antagonists 2. Current antidepressant medications (all classes) or use within the past 30 days 3. Recent use (multiple consecutive doses) of systemic corticosteroids 4. Needing to use antihistamines, aspirin (other than low-dose ASA for prophylactic purposes), non-steroidal anti-inflammatory drugs (NSAIDs), or systemic corticosteroids, on Study Visit days 5. Use of any other medication that in the judgment of the PI would increase risk of study participation or introduce excessive variance into physiological or behavioral responses to WBH 6. Regular use of any nicotine products, including cigarettes, vapes, chewing tobacco, or other forms of nicotine 7. The following medications in these timeframes: Antibiotics (past 14 days), Pain medication (opioids) due to procedure, e.g., dental procedure (past 14 days), Emergency contraception pill (past 14 days)

EFFICACY EVALUATIONS	See below for primary and secondary endpoints.

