PRIMARY ENDPOINT	Primary outcomes. The primary endpoint is study acceptability, as indexed by participant-reported net-promoter scores, which will range from 0 (would not recommend) to 10 (would definitely recommend).
SECONDARY ENDPOINTS	Secondary outcomes. We will assess pre-post intervention changes in: Beck Depression Inventory (BDI-II), Patient-Reported Outcome Measurement System (PROMIS) Depression, PROMIS Anxiety, and the Hamilton Depression Rating Scale (HAMD-6).
OTHER EVALUATIONS	N/A
SAFETY EVALUATIONS	Incidence of unexpected adverse events. We will monitor participants for unexpected adverse events and serious adverse events during and following the sauna sessions.
PLANNED INTERIM ANALYSES	Due to the current study design and safety profile of this test product (portable sauna dome – one person) and cognitive behavioral therapy (CBT; a standard depression psychotherapy treatment), we do not plan any interim analyses.
STATISTICS Primary Analysis Plan	
Primary outcome: We assessed study acceptability by computing means and standard deviations of participant-reported net-promoter scores, which will range from 0 (would not recommend) to 10 (would definitely recommend).
 
Note on Original Primary Outcome: Although we collected and reported this outcome, participants noted that they may not have recommended the study as highly to others because antidepressant medication use was an exclusion criteria, and many participants knew that their friends or family members used these medications. Because that awareness may have biased net promotor scores downward, we report an additional acceptability measure.
 
Revised Additional Primary Outcome: A second study acceptability measure asked participants how likely they would be to enroll in the study given their experience in the study, on a scale from 1 (extremely unlikely to enroll) to 5 (extremely likely to enroll). We reported the score mean and standard deviation.
 
Secondary outcomes: We assessed change in scores on the Beck Depression Inventory (BDI-II), Patient-Reported Outcomes Measurement Information Systems (PROMIS) measures, and Hamilton Depression Rating Scale (HAMD-6), using T-Tests, and report the mean changes and associated standard errors. Units for PROMIS measures are T-Score points.

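### The secondary depression and anxiety scales are analysed as pre-post changes with t-tests of unstated type, and no active-minus-sham estimate is named.

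*Combined protocol and SAP*

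**What the plan says.** Under SECONDARY ENDPOINTS the plan writes "We will assess pre-post intervention changes in: Beck Depression Inventory (BDI-II" and goes on to PROMIS Depression, PROMIS Anxiety and HAMD-6. The whole analysis of these scales is one sentence on change scores in STATISTICS, Primary Analysis Plan, ending "Hamilton Depression Rating Scale (HAMD-6), using T-Tests, and report the mean changes and associated standard errors", plus a note on PROMIS units. Neither place mentions the arms.

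The design is a 1:1 randomized sham comparison. Under CONTROL PRODUCT: "All participants receive cognitive behavioral therapy (CBT), and 50% of participants receive active sauna sessions while 50% receive sham sauna sessions".

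On what counts as the pre score:
- PARTICIPANT SELECTION CRITERIA requires a "Beck Depression Inventory-II (BDI-II) score ≥ 21 at screening" and excludes anyone with a more than 30% "reduction in BDI-II score between Screen #1 and Screen #2 (conducted ~ 1 week after Screen #1").
- The in-person screening and baseline visit has participants "complete self-report questionnaires, anthropometric assessments, schedule study visits. Randomization to receive either active sauna sessions or sham sauna sessions".
- At closeout the plan has the "participant to complete questionnaires, complete clinician-administered assessment, provide blood and saliva samples, and return Oura ring".

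On purpose, SECONDARY OBJECTIVES reads: "To pilot test the feasibility of all assessment procedures in anticipation of a larger trial".

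**The concern.** Sauna is the only thing that differs between the randomized arms. The BACKGROUND section describes CBT as efficacious, so improvement is expected in both arms whether or not sauna adds anything. On these four scales only the between-arm difference reflects sauna, and the plan does not name it.

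The consequence depends on which t-test is meant:

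1. **Paired, pooled over arms.** The change mixes CBT, sauna or sham, natural course and residual regression to the mean, and says nothing about sauna. Regression to the mean arises because entry requires a BDI-II of at least 21. The re-screen exclusion limits it without removing it, and it acts only indirectly on PROMIS Anxiety.
2. **Paired, within each arm.** Neither test isolates sauna. A reader can derive the arm difference from the two means and standard errors, but is invited to compare p-values instead.
3. **Two-sample on change.** This is valid and unbiased, though usually less precise than an analysis of covariance (ANCOVA).

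The pilot is meant to prepare a larger efficacy trial, so a reader of the results needs to know which quantity was reported.

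**Working it through.** **The plan's own figure.** The only computed figure is the acceptability interval under Rationale for Number of Participants: 25/30 ± 1.96 × √(0.833 × 0.167 / 30) gives 70.0% to 96.7%, matching the stated 70% to 97%. It concerns the primary endpoint. The documents give no SD, correlation, alpha or effect size for the secondary scales.

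**Inputs.** From the documents: N=30, allocated 1:1, hence 15 per arm. Assumed: complete data, two-sided alpha 0.05, no sauna effect, and a common improvement d of 0.5 to 0.8 SD of change in both arms.

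**Standard errors, in SD-of-change units**
- Pooled change: 1/√30 = 0.183; 95% half-width 0.373 (29 df).
- One arm: 1/√15 = 0.258.
- Active minus sham: √(1/15 + 1/15) = 0.365; half-width 0.748 (28 df). With 12 completers per arm the half-width would be about 0.85.

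**Chance of significance when sauna does nothing.** For the paired tests, the noncentral t has n−1 df and noncentrality d√n.

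| Analysis | d = 0.5 | d = 0.8 |
|---|---|---|
| Pooled paired, n=30 | 0.754 | 0.988 |
| Paired in one arm, n=15 (p) | 0.438 | 0.821 |
| Exactly one arm significant, 2p(1−p) | 0.492 | 0.294 |
| Active arm only, p(1−p) | 0.246 | 0.147 |
| Two-sample on change | 0.05 | 0.05 |

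A simulation of 200,000 trials agreed: pooled 0.756 and 0.989, exactly one arm 0.494 and 0.293, two-sample 0.050 and 0.051.

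The pooled figures are power for a real overall improvement, not an error rate. They mislead only if read as a sauna effect.

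**ANCOVA against two-sample change.** Let r be the baseline-to-closeout correlation and k the baseline SD divided by the closeout SD; both are assumptions. The ratio of variances (ANCOVA over change) is (27/26)(1−r²)/(1 + k² − 2rk), where 27/26 is the cost of estimating the covariate slope with 30 participants. For k=1 and r=0.5: 1.038 × 0.75 / 1 = 0.779. The reciprocal, in brackets, is the equivalent multiple of the sample size.

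| k | r = 0.3 | r = 0.5 | r = 0.7 |
|---|---|---|---|
| 0.7 | 0.883 (1.13) | 0.986 (1.01) | 1.038 (0.96) |
| 0.8 | 0.815 (1.23) | 0.927 (1.08) | 1.018 (0.98) |
| 1.0 | 0.675 (1.48) | 0.779 (1.28) | 0.883 (1.13) |

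Simulated ratios agreed to within about 0.002.

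At r=0.5 the half-width for change, in closeout SD, is 0.748 × √(1 + k² − k): 0.665, 0.686 and 0.748 for k = 0.7, 0.8 and 1. For ANCOVA it is 0.661 (27 df) throughout.

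**The case against.** The strongest reply is that this is an omission, not a wrong analysis. A two-sample t-test of change by arm fits the wording and would be sound. Even paired tests by arm would let a reader reconstruct the difference. Only the pooled reading hides the sauna contrast, and nothing shows that it was used. The stated objectives are feasibility and acceptability, the sample size rests on one pooled proportion, and no efficacy hypothesis is stated. All of this stands and limits the stakes. However, the EFFICACY EVALUATIONS row points to these endpoints, and the plan already commits to testing them.

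It can also be said that the 49% to 29% figure overstates the risk, because only the active-arm-only pattern (25% to 15%) would falsely favour sauna, and the plan does not propose to interpret such a pattern. The halving is right for that direction. The two-sided 5% counts both directions too, so the comparison is like with like. It remains a warning about reading within-arm p-values, not a claim that the plan does so.

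The gain from ANCOVA is modest and rests on assumptions. Entry truncated at a BDI-II of 21 may well shrink the baseline SD, and that is where the gain is smallest. This stands: naming the arm difference matters more than the adjustment.

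On HAMD-6, defining it as a pre-post change implies a baseline value, and the selection criteria mention a clinician-administered interview. That interview is not said to include HAMD-6, and the closeout list does not name the scale either, so asking for confirmation is fair.

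**Conclusion.** The point holds with high confidence as an omission: the type of t-test is unstated and no between-arm estimate appears anywhere in the document. Which analysis was intended cannot be determined, so the consequence ranges from none of substance (two-sample) to a result that carries no information on sauna (pooled paired). The twofold range in the standard error follows from N=30 and 1:1 allocation with complete data and equal SDs of change. The significance probabilities also assume a common improvement of 0.5 to 0.8 SD. ANCOVA would be worth between 0.96 and 1.48 times the sample for r of 0.3 to 0.7 and SD ratios of 0.7 to 1.

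This should be put right, but it does not threaten the pilot's main purpose or its primary acceptability outcome. With a half-width near 0.75 SD of change, the arm difference will be imprecise, and it should be presented as an estimate, not as evidence for or against efficacy.

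**What to change.** - State which t-test is used: paired or two-sample, pooled or by arm.
- For each of the four scales, add an ANCOVA of the closeout score on arm and the last score recorded before randomization. Report the active-minus-sham difference with its 95% CI as an estimate, not an efficacy test.
- Give mean changes and standard errors by arm as description, and draw no conclusion about sauna from within-arm p-values.
- For BDI-II, name the baseline score: Screen #1, Screen #2 or the baseline visit.
- For HAMD-6, confirm that a pre-randomization score exists. The baseline visit's list does not name it, while closeout includes a clinician-administered assessment.
- The analysis text is partly in the past tense. If the t-test results are already known, keep them and label the ANCOVA post hoc.

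The cost is four regressions on scores that the change analysis already needs, and a few sentences. The downsides are a possible small loss of precision (up to about 4% in variance in the cases computed, when the baseline SD is small and r is high) and the weaker standing of a post hoc analysis if results are already known.

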Rationale for Number of Participants	The primary endpoint is participant-reported net-promoter scores, which will range from 0 (would not recommend) to 10 (would definitely recommend). If 25 of 30 Aim 2 participants rate the study experience > 7 (83%), the 95% CI will be 70% to 97% (normal approximation to the binomial), which we also believe will provide

	adequate precision for feasibility/acceptability testing.
--	-----------------------------------------------------------

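### The 95% interval behind N = 30 (70% to 97% for 25 of 30) is a Wald interval: it sits too high and falls short of 95% coverage, and the lower limit should be about 65% to 66%

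*Combined protocol and SAP*

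**What the plan says.** The trial is described under Duration of Participant Participation and Duration of Study as a "single-center, two-arm, randomized experimental study that will include 30 participants". The section Rationale for Number of Participants supports that number with one worked example, the only precision statement for N in the document. The premise is "If 25 of 30 Aim 2 participants rate the study experience > 7 (83"%), the result is that "the 95% CI will be 70% to 97% (normal approximation to the binomial"), and the conclusion is that this gives "adequate precision for feasibility/acceptability testing".

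The section sets no minimum acceptable proportion and no criterion for the lower limit. The Primary Analysis Plan under Statistics handles the primary outcome differently: "We assessed study acceptability by computing means and standard deviations of participant-reported net-promoter scores". It mentions neither the proportion above 7 nor a binomial confidence interval.

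**The concern.** The normal approximation to the binomial is weak when one of the two categories is small. In the example, 5 of 30 participants fall in the smaller one. The Wald interval is centred on the observed proportion and is symmetric. For a proportion near 83% on 30 people, an interval that holds its level is pulled towards 50%, with a longer arm on the lower side. The stated limits can therefore be expected to lie too high and to miss mostly in the favourable direction.

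At stake is how a reader interprets the example. The trial prepares for a larger efficacy trial, and this interval is the document's only guide to what a result of 25 of 30 would show. A reader would take 70% as the lower end of the plausible range at 95% confidence.

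**Working it through.** **Inputs.** n = 30, x = 25, p = 25/30 = 0.8333, 95% two-sided (z = 1.96), all from Rationale for Number of Participants. No dropout figure is given for this calculation, so n = 30 is used as stated.

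**1. The plan's figure.** Wald: p ± z·√(p(1−p)/n).

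- √(0.8333 × 0.1667 / 30) = 0.0680, and 1.96 × 0.0680 = 0.1334.
- Limits: 0.8333 ± 0.1334 = 0.7000 to 0.9667.

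This matches the stated 70% to 97%. With a continuity correction of 1/(2n) the limits would be 68.3% to 98.3%, which do not match, so the plan used the plain Wald interval.

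**2. Alternatives for 25/30.** Wilson has centre (p + z²/2n)/(1 + z²/n) and half-width [z/(1 + z²/n)]·√(p(1−p)/n + z²/4n²). With z² = 3.8415:

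- Centre: (0.8333 + 0.0640)/1.1280 = 0.7955.
- Half-width: (1.96/1.1280) × √(0.00463 + 0.00107) = 0.1311.
- Limits: 0.6644 to 0.9266.

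Clopper-Pearson (exact) takes the 2.5% quantile of Beta(25, 6) and the 97.5% quantile of Beta(26, 5).

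| Method | Lower | Upper | Width (points) |
|---|---|---|---|
| Wald (plan) | 70.0% | 96.7% | 26.7 |
| Wilson | 66.4% | 92.7% | 26.2 |
| Clopper-Pearson | 65.3% | 94.4% | 29.1 |

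The stated lower limit is 3.6 points above Wilson and 4.7 above exact. The stated upper limit is 4.0 and 2.3 points higher.

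**3. Coverage at a true proportion of 25/30.** Sum Binomial(30, 25/30) probabilities over the results whose Wald interval misses 0.8333.

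- The lower limit exceeds 0.8333 from x = 28 (limit 0.8441). P(X ≥ 28) = 0.0733 + 0.0253 + 0.0042 = 0.1028.
- The upper limit is below 0.8333 up to x = 19 (at x = 20 it is 0.8354). P(X ≤ 19) = 0.0067.
- Coverage = 1 − 0.1028 − 0.0067 = 0.8905, or about 89%, against a nominal 95% with 2.5% in each tail.

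Wilson and Clopper-Pearson both cover 97.6% at this value.

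**4. Coverage at other true proportions, n = 30, Wald.**

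| True proportion | Coverage | Interval above truth | Interval below truth |
|---|---|---|---|
| 0.75 | 94.1% | 3.7% | 2.2% |
| 0.80 | 94.6% | 4.4% | 0.9% |
| 25/30 | 89.0% | 10.3% | 0.7% |
| 0.85 | 94.2% | 4.8% | 1.0% |
| 0.90 | 80.9% | 18.4% | 0.8% |
| 0.95 | 78.2% | 21.5% | 0.3% |

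Over an even grid from 0.70 to 0.95, Wald averages 90.7%, with mean misses of 8.2% above the truth and 1.2% below. Wilson averages 95.4% on the same grid, and Clopper-Pearson is at least 95% throughout.

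**5. Direct check of the lower limit.** If the true proportion were exactly 70%, 25 or more of 30 would score above 7 with probability 7.7%. A 95% interval whose lower limit is 70% implies about 2.5%.

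**6. Higher results.** The Wald upper limit exceeds 100% at 27, 28 and 29 of 30 (100.7%, 102.3% and 103.1%). At 30 of 30 both limits equal 100% and the width is zero.

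**The case against.** The best defence is that nothing was miscalculated or hidden. The figure reproduces, the approximation is named, and the example is a hypothetical planning illustration for a 30-person pilot. All of that is true, but naming the method does not give the interval the 95% level attached to it.

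Three further objections limit the point:

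- **Width.** A reader might infer that the plan overstates its precision. The documents do not support that: the stated width of 26.7 points is slightly more than Wilson's 26.2, and only the exact interval, which is conservative by construction, is wider (29.1). The plan's judgement that the precision is adequate does not fail on this ground.
- **Decisions.** A reader might infer that a ruling-out claim or a go/no-go decision rests on the 70% limit. The document contains no acceptability threshold and does not say that any value is excluded, so moving the limit to 65% or 66% changes no stated decision.
- **Reporting.** A reader might infer that the trial's results will be reported with this faulty interval. The Primary Analysis Plan gives means and standard deviations, so the behaviour at 27 to 30 of 30 matters only if a proportion is added.

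The coverage shortfall also varies with the true value. It is small at 0.75, 0.80 and 0.85, and the misses are not equally one-sided everywhere: about 94% are favourable at 25/30, against an average of about 87% over 0.78 to 0.88. The shortfall is still the rule, as the 90.7% average shows.

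**Conclusion.** The point holds as one of location and confidence level. For 25 of 30, the stated interval lies 2 to 5 points too high at each end against the Wilson and exact intervals, and its lower limit should be about 65% to 66%. Its actual coverage is about 89% if the true proportion is the 83% used in the example. These figures rest on all 30 participants contributing a score, on independent responses, and on the stated cut of above 7.

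The practical impact is minor. The sentence is wrong as written, and it matters because it is the only quantitative support for N = 30. The check gives no reason to change N, and no reason to doubt the planned mean and standard deviation.

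**What to change.** In Rationale for Number of Participants, replace the stated limits and method with either 66% to 93% (Wilson) or 65% to 94% (exact, Clopper-Pearson). If a proportion scoring above 7 is reported from the 30 participants, use the same method for its interval.

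The cost is one sentence. N, the design and the planned analysis stay as they are. The only downside is a slightly less favourable stated lower limit.
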